6.6 Data Linkage

The participant's NHS number or CHI number will be collected to allow future linkage with national data registries such as NHS Digital, Public Health England, the Information Services Division (part of NHS Scotland), or the electronic Data Research and Innovation Service (eDRIS). For the HSCT participant group the British Society of Blood and Marrow Transplantation (BSBMT) registry identification (PROMISE ID) will also be collected, where participants have also consented to collection of data within this registry, to allow for data linkage. Data linkage will provide a more complete profile of the participants' health and disease without increased data collection burden to the NHS.

6.7 Participant Withdrawal

Participants may withdraw consent at any time during the trial. For the purposes of this trial two types of withdrawal are defined:

- The participants would like to withdraw from further sample collection but is willing to be followed up as standard (i.e. the patient has agreed that data can be collected at standard clinic visits and used in the analyses)
- The participants would like to withdraw from the trial entirely and is not willing to be followed up for the purposes of the trial (i.e. only data and samples collected prior to the withdrawal of consent can be used in the trial analysis) withdrawal of consent

The details of withdrawal (date, reason and type of withdrawal) should be clearly documented in the source data. A Withdrawal of Consent Form should be completed to notify the Trial Office of the participant's withdrawal from the trial.

7. ADVERSE EVENT REPORTING

The collection and reporting of Adverse Events (AEs) will be in accordance with the Medicines for Human Use Clinical Trials Regulations 2004 and its subsequent amendments. Definitions of different types of AE are listed in Appendix 1. The seriousness and causality (relatedness) of all AEs experienced by the participant should be assessed with reference to the relevant information for healthcare professionals (see Section 7.1).

7.1 Reporting Requirements

7.1.1 Adverse Events

AEs are commonly encountered by participants with the chronic healthcare conditions being studied in this trial. Hence only Adverse Reactions (ARs) thought to be related to the administration of the SARS-CoV-2 vaccines will be collected.

7.1.2 Serious Adverse Events

Investigators should only report AEs that meet the definition of an SAE and which are thought to be related to the administration of the SARS-CoV-2 vaccine. These events should be reported on a SAE Form as described in Section 8.3.1.2.

Page 18 of 40 v6.0, 14-Jul-2021

7.2 Reporting Period

Details of AEs will be documented and reported from the date of recruitment into the OCTAVE trial and only after the initial vaccination of SARS-CoV-2 vaccine until 28 days after the administration of the booster.

SAEs that are judged to be at least possibly related to the IMP and are unexpected must still be reported in an expedited manner irrespective of how long after IMP administration the reaction occurred.

7.3 Reporting Procedure

7.3.1 Site

7.3.1.1 Adverse Events

For more detailed instructions on AR reporting refer to the CRF Completion Guidelines contained in the Investigator Site File.

ARs experienced following vaccination should be recorded on the Vaccination Form.

ARs will be graded using the Common Terminology Criteria for Adverse Events (CTCAE), version 4.03 (see Appendix 2).

Any ARs experienced by the participant but not included in the CTCAE should be graded by an investigator and recorded using a scale of (1) mild, (2) moderate or (3) severe.

For each AR, the highest grade should be recorded.

7.3.1.2 Serious Adverse Events

For more detailed instructions on SAE reporting refer to the SAE Form Completion Guidelines contained in the Investigator Site File.

AEs defined as serious which are thought to be related to SARS-CoV-2 vaccination and which require reporting as an SAE should be reported on an SAE Form. When completing the form, the investigator will be asked to define the causality and the severity of the AE which should be documented using CTCAE version 4.03.

The form should be emailed to the Trial Office as soon as possible and no later than 24 hours after first becoming aware of the event:

Send SAEs to

[contact]

Cc [contact]
Include "OCTAVE SAE" in the subject line

be quoted on all correspondence and follow-up reports regarding the SAE. The email from the Trial Office acknowledging receipt should be filed with the SAE Form in the Investigator Site File.

Page 19 of 40 v6.0, 14-Jul-2021

CRCTU-PRT-QCD-001, version 1.0

For SAE Forms completed by someone other than the investigator the investigator will be required to countersign the original SAE Form to confirm agreement with the causality and severity assessments. The form should then be returned to the Trial Office and a copy kept in the Investigator Site File.

Investigators should also report SAEs to their own Trust or Health Board in accordance with local policy.

Provision of follow-up information

Participants should be followed up until resolution or stabilisation of the event. Follow-up information should be provided on a new SAE Form (refer to the SAE Form Completion Guidelines for further information).

7.3.2 OCTAVE Trial Office

On receipt of an SAE Form, causality and expectedness will be determined by a Clinical Coordinator. An SAE judged by the investigator or Clinical Coordinator to have a reasonable causal relationship with the trial medication will be regarded as a Serious Adverse Reaction (SAR). If the event meets the definition of a SAR that is unexpected (i.e. is not listed in the Reference Safety Information) it will be classified as a Suspected Unexpected Serious Adverse Reaction (SUSAR).

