The OCTAVE trial is a multi-centre, multi-disease, prospective observational cohort trial of the immune response to SARS-CoV-2 vaccination. We will evaluate immunity arising from receipt of the COVID-19 Vaccine AstraZeneca, COVID-19 mRNA Vaccine BNT162b2 and COVID-19 Vaccine Moderna or other MHRA approved SARS-CoV-2 vaccines implemented in the UK. Participants with end stage kidney disease, liver disease, cancer, immune-mediated rheumatic diseases, and transplant recipients attending specialist clinics across the UK will be recruited. If funding permits additional disease cohorts may also be added by protocol amendment if scientifically and clinically relevant to the objectives of the trial.

Cohorts of approximately 100 to 200 participants depending on disease group will be recruited for full immune response analysis ("Deep Immunophenotyping Group"). Additional participants will be recruited, between 150 and 850 depending on disease group, for serology analysis ("Serology Group"). Up to 3250 participants will be recruited in total.

Additional vaccine response studies are ongoing across the UK, including Department of Health and Social Care funded analyses of responses in health care workers, care homes, and in BAME groups. Through use of common immune assay platforms, our data will be directly comparable with these emerging datasets allowing comparison with matched controls.

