7.3.3 Reporting to the Competent Authority and Research Ethics Committee

7.3.3.1 Suspected Unexpected Serious Adverse Reactions

The Trial Office will report a minimal data set of all individual events categorised as a fatal or life threatening SUSAR to the MHRA and REC within 7 days. Detailed follow-up information will be provided within an additional 8 days.

All other events categorised as SUSARs will be reported within 15 days.

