An Adverse Reaction which also meets the definition of a Serious Adverse Event.

Suspected Unexpected Serious Adverse Reaction (SUSAR)

A SAR that is unexpected i.e. the nature, or severity of the event is not consistent with the applicable product information.

A SUSAR should meet the definition of an AR, UAR and SAR.

Unexpected Adverse Reaction (UAR)

An AR, the nature or severity of which is not consistent with the Reference Safety Information.

When the outcome of an AR is not consistent with the Reference Safety Information, the AR should be considered unexpected.

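### Section 7.3.2 tests expectedness by listing alone while Appendix 1 also counts inconsistent severity or outcome, so a listed but worse serious reaction could miss the 7-day or 15-day report

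*Protocol*

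**What the plan says.** Section numbers here follow the body of the protocol; the table of contents numbers the adverse event section one higher.

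Section 7.3.2 makes the decision at the Trial Office: "On receipt of an SAE Form, causality and expectedness will be determined by a Clinical Coordinator". A serious reaction becomes a SUSAR when it is a "SAR that is unexpected (i.e. is not listed in the Reference Safety Information"). Severity and outcome are not part of that test.

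Appendix 1 defines the same class differently. Its SUSAR entry reads: "A SAR that is unexpected i.e. the nature, or severity of the event is not consistent with the applicable product information". Its entry for an unexpected adverse reaction reads: "An AR, the nature or severity of which is not consistent with the Reference Safety Information", and adds: "When the outcome of an AR is not consistent with the Reference Safety Information, the AR should be considered unexpected". Appendix 1 also requires a SUSAR to satisfy the definition of an unexpected adverse reaction.

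The classification sets the reporting route. Under 7.3.3.1 the Trial Office reports "all individual events categorised as a fatal or life threatening SUSAR to the MHRA and REC within 7 days", with detailed follow-up in a further 8 days; other SUSARs go within 15 days. Under 7.3.3.2 all serious reactions, SUSARs included, appear in the annual DSUR. Under 7.3.3.4 Principal Investigators are told of all SUSARs and of any other safety issue.

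**The concern.** Two parts of one protocol define the same word, and the narrower definition sits in the operating instruction. With its *i.e.*, the bracket in 7.3.2 reads as the full meaning of unexpected, not as an example of it. A coordinator who follows it literally asks only whether the reaction appears in the reference text.

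Much depends on this one decision. Sites are asked to report only serious events thought to be related to the vaccine (7.1.2), so most events that reach the Trial Office have already been judged related. Expectedness is then the main remaining step before an expedited report. Section 7.2 also makes expedited reporting of late related events depend on whether they are unexpected. Section 11.5 states that there is no independent oversight committee, so reports to the MHRA and REC are a main outside check on individual events.

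**Working it through.** No arithmetic applies and the protocol gives no figure to reproduce. The check is to run the possible kinds of related serious event through both definitions and then through the reporting rules.

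Inputs: the listing test (7.3.2); the nature, severity and outcome tests (Appendix 1); 7 and 15 days for SUSARs (7.3.3.1); annual reporting for serious reactions in general (7.3.3.2).

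| Related serious event | 7.3.2, read literally | Appendix 1 | Report to MHRA and REC |
|---|---|---|---|
| Not in the reference text | Unexpected | Unexpected (nature) | 7 or 15 days under both |
| Listed; severity and outcome as described | Expected | Expected | Annual under both |
| Listed; severity not consistent; not fatal or life-threatening | Expected | Unexpected (severity) | Annual under 7.3.2; 15 days under Appendix 1 |
| Listed; life-threatening, severity not consistent | Expected | Unexpected (severity) | Annual under 7.3.2; 7 days under Appendix 1 |
| Listed; fatal, outcome not consistent | Expected | Unexpected (outcome) | Annual under 7.3.2; 7 days under Appendix 1 |

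The definitions agree in the first two rows and diverge in the last three.

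The severity rows rest directly on the SUSAR entry in Appendix 1. The outcome row takes one more step: the outcome sentence stands under the unexpected adverse reaction, and it reaches SUSARs because a SUSAR must also satisfy that definition.

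Size of the delay: the interval between annual reports is about 12 months. An event that falls just after one report could therefore wait up to about 12 months for the next, against 7 or 15 days. That is the upper end; an event shortly before an annual report would wait much less.

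Is there a rule of precedence? The opening of section 7 says that the definitions of adverse event types are in Appendix 1. Neither that sentence nor anything in 7.3.2 to 7.3.3.2 says which text governs when they differ.

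**The case against.** The strongest reply is that the protocol already leads the reader to the wider test. Section 7 opens by pointing to Appendix 1 and by placing reporting under the clinical trials regulations. Section 7.3.2 speaks of an event meeting a definition, and the definitions are in Appendix 1. A careful coordinator could treat the bracket as shorthand. This has real weight, and it is why the conclusion is that a report could be missed, not that it would be. It does not remove the conflict, because the operating instruction states its own test and no text ranks the two.

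A second reply is that a reference document may list reactions with their severity or outcome. A fatal form would then simply not be listed, and the two tests would agree. That is correct as far as it goes. The reference documents are not part of the protocol, so how often the tests would diverge cannot be determined. The divergence arises where the reference text names a reaction without that qualification.

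Other channels also remain. Sites report serious events to the Trial Office within 24 hours and to their own Trust or Health Board (7.3.1.2), adverse event details go to the MHRA on request (7.3.3.3), and Principal Investigators can be told of other safety issues (7.3.3.4). The gap therefore concerns onward expedited reporting, not whether the Trial Office learns of the event.

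A reader might infer three stronger points that the protocol does not support:

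- The Trial Design section admits the three named vaccines "or other MHRA approved SARS-CoV-2 vaccines implemented in the UK", while 6.1 links product information for those three only. It is tempting to conclude that reactions to another vaccine would be under-reported. The listing test works the other way: with no list, every serious reaction is not listed and so unexpected.
- These cohorts were chosen for impaired immunity, so a known reaction in a worse form might seem the signal the trial is most likely to meet. The background section argues that protection may be weaker; it makes no prediction about worse reactions.
- The name of the reference text varies. No different classification is shown to follow from that, so the variation is editorial.

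**Conclusion.** The point holds as a wording conflict in a safety-reporting rule. For a related serious reaction that is listed, but whose severity or outcome does not fit the reference text, the literal 7.3.2 test gives annual reporting and Appendix 1 gives 7 or 15 days. At the upper end the difference is up to about 12 months.

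This rests on two assumptions: that the coordinator applies the bracket in 7.3.2 as written, and that the reference text names the reaction without limiting it by severity or outcome. Neither can be confirmed or excluded from the protocol. Nothing shows that any event has been misclassified, and the number of events affected cannot be estimated. The correction is worth making because it is cheap and the sponsor's own wider wording already exists in Appendix 1.

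**What to change.** Reconcile 7.3.2 with Appendix 1. Replace the bracket in 7.3.2 with the protocol's own Appendix 1 test: a serious reaction is unexpected if its nature, severity or outcome is not consistent with the Reference Safety Information. Use that one term for the reference text in 7.3.2 and throughout Appendix 1, including the SUSAR entry, which now refers to product information.

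The cost is a few words in two places. Severity is already recorded on the SAE Form (7.3.1.2), so the severity test needs no new data. The downside is possibly a few more expedited reports.

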7.3.3 Reporting to the Competent Authority and Research Ethics Committee

7.3.3.1 Suspected Unexpected Serious Adverse Reactions

The Trial Office will report a minimal data set of all individual events categorised as a fatal or life threatening SUSAR to the MHRA and REC within 7 days. Detailed follow-up information will be provided within an additional 8 days.

All other events categorised as SUSARs will be reported within 15 days.

7.3.3.2 Serious Adverse Reactions

The Trial Office will report details of all SARs (including SUSARs) to the MHRA and REC annually from the date of the Clinical Trial Authorisation (CTA), in the form of a Development Safety Update Report (DSUR).

7.3.3.3 Adverse Events

Details of all AEs will be reported to the MHRA on request.

7.3.3.4 Investigators

Details of all SUSARs and any other safety issue which arises during the course of the trial will be reported to Principal Investigators. A copy of any such correspondence should be filed in the Investigator Site File.

9. DATA COLLECTION

The CRF will be comprised of the forms listed in Table 2.

Page 20 of 40 v6.0, 14-Jul-2021

Table 2: OCTAVE Trial Case Report Form

	Form	Summary of Data Recorded*	Schedule for Submission to Trial Office	
Registration		Minimal identifiers (initials and date of birth)	Complete at trial entry	
Baseline		NHS/CHI/ BSBMT registry ID, hospital number, demographic data (sex, ethnicity), World Health Organisation (WHO) performance status (Appendix 3), body mass index, medical history including comorbidities, disease group specific information (including disease status), details of prior COVID-19 infection, collection of baseline research samples	Within 1 month of trial entry	
Treatment Form	First vaccination Second vaccination	Details of rituximab, corticosteroids, and nonsteroidal anti-inflammatory drugs (NSAIDs) and other disease cohort specific	As soon as possible after relevant vaccination	
Vaccination form	First vaccination	treatments Date of vaccination Type of vaccination Batch number (if known) Planned date of booster (if known)	As soon as possible after relevant vaccination	
	Second vaccination	Date of booster Type of vaccination Batch number (if known)		
Vaccination Adverse Reaction	First vaccination	Details of ARs thought to be related to SARS-CoV-2	As soon as possible after relevant vaccination	
Form	Second vaccination	vaccination	relevant vaccination	
Research San	nple Collection Form	Confirmation of collection of research samples in accordance with the protocol	As soon as possible on collection of research samples	
Follow-up		Survival data, COVID-19 infection data, WHO performance status, disease site specific	Six months post second vaccination (booster) and 12 months post first vaccine or third vaccination	

Page 21 of 40 v6.0, 14-Jul-2021

Form	Summary of Data Recorded*	Schedule for Submission
		to Trial Office
Death	Date and cause of death	Immediately upon notification
Death	Date and cause of death	of participant's death
	Used to notify the Trial Office of	Immediately upon patient
Withdrawal of Consent	the participant's withdrawal from	withdrawal
	the trial	Withdrawai
	Details on deviations from the	Immediately upon discovery of
Deviation Form	protocol not captured elsewhere	a deviation
	on the CRF	a deviation
	Details of any SAE thought to be	No later than 24h after
Serious Adverse Event	related to SARS-CoV-2	
	vaccination	becoming aware of the event

^{*} It is anticipated data will collected retrospectively from the participants medical records.

This trial will use an eRDC system to capture the CRF data, the only exception to this will be the registration data which will be captured in an Excel workbook (a paper version of the Registration Form is also available) and the SAE Form which will be completed on paper.

Access to the eRDC system will be granted to site research staff by the Trial Office.

https://crctu.redcap.bham.ac.uk/

The investigator and site staff will ensure all data is promptly entered into the eRDC system in accordance with the trial specific User Manual and CRF Completion Guidelines. The CRF must be completed by the investigator or an authorised member of the site research team (as delegated on the Site Signature and Delegation Log).

Entries on the paper CRF should be made in ballpoint pen, in blue or black ink, and must be legible. Any errors should be crossed out with a single stroke, the correction inserted and the change initialled and dated. If it is not obvious why a change has been made, an explanation should be written next to the change.

Data reported on the CRF should be consistent with the source data or the discrepancies should be explained. If information is not known, this must be clearly indicated on the form. All missing and ambiguous data will be queried. All sections are to be completed before returning.

In all cases it remains the responsibility of the investigator to ensure that the CRF has been completed correctly and that the data are accurate.

The CRF may be amended from time to time by the Trial Office throughout the duration of the trial. Whilst this will not constitute a protocol amendment, new versions of the CRF must be implemented by participating sites immediately on receipt.

Page 22 of 40 v6.0, 14-Jul-2021

7.4 Archiving

It is the responsibility of the Principal Investigator to ensure all essential trial documentation and source records (e.g. signed Informed Consent Forms, Investigator Site Files, participants' hospital notes, etc.) at their site are securely retained for at least 10 years after the end of the trial. Do not destroy any documents without prior approval from the CRCTU Archivist.

8. QUALITY MANAGEMENT

8.1 Site Set-up and Initiation

All sites will be required to sign a model Clinical Trials Agreement (mNCA) prior to participation. In addition, all participating investigators will be asked to sign the necessary agreements e.g. Registration Forms and supply a current *curriculum vitae* (CV) to the Trial Office. Prior to commencing recruitment all sites will undergo a process of initiation. Site initiation meetings will be held on request. Where these are held, key members of the site research team will be invited to attend a teleconference covering aspects of the trial design, protocol procedures, collection and reporting of data and record keeping. Sites will be provided with the documentation for an Investigator Site File containing essential documentation, instructions, and other documentation required for the conduct of the trial. The Trial Office must be informed immediately of any change in the site research team.

8.2 On-site Monitoring

Monitoring will be carried out as required following a risk assessment and as documented in the OCTAVE Quality Management Plan. Additional on-site monitoring visits may be triggered for example by poor CRF return, poor data quality, low SAE reporting rates, excessive number of patient withdrawals or deviations. If a monitoring visit is required the Trial Office will contact the site to arrange a date for the proposed visit and will provide the site with written confirmation. Investigators will allow the OCTAVE trial staff access to source documents as requested.

8.3 Central Monitoring

The Trial Office will be in regular contact with the site research team to check on progress and address any queries that they may have. Trial staff will check incoming CRF for compliance with the protocol, data consistency, missing data and timing. Sites will be sent queries through the REDCap system requesting missing data or clarification of inconsistencies or discrepancies.

Sites may be suspended from further recruitment in the event of serious and persistent non-compliance with the protocol and/or Good Clinical Practice (GCP). Any major problems identified during monitoring may be reported to the Trial Management Group (TMG) and the relevant regulatory bodies. This includes reporting serious breaches of GCP and/or the trial protocol to the REC (see Section 9.5 for further details).

Page 23 of 40 v6.0, 14-Jul-2021

